#### Schedule of visits and evaluations

Visit Description						
Study Visits: Days or Weeks	Screening Visit	Additional Screening *meets criteria -2.5≤T≤+1	Baseline Visit	6 Month Visit	12 Month Visit	Study Completion
Informed Consent	X					
Demographics	X					
Medical History	X					
Prior Medications	X					
Height	X					
Weight	X					
Urine Pregnancy Test	X					

DXA Hip and Spine	X				X	
pQCT		X			X	
Blood Draw		X				
MRI Tibia and Spine			X		X	
Randomization			X			
Subject Instructed to Begin Use of Device			X			
Data Collection from Device				X	X	
Start Vitamin D3 and Calcium Carbonate			X			
Review Medical Status, supplement compliance and Daily Routine				X	X	
Adverse Events		X	X	X	X	X
Study Completion						X

#### Training plan

All study personnel have completed the CITI training program and certificates are filed in the regulatory binders. A delegation of responsibilities log has been created and is also filed in the regulatory binder. Study team meetings will be held regularly at the University of Pennsylvania to assure all study personnel are adhering to the protocol. Sub groups will meet as needed.

#### Recruitment, screening, and eligibility criteria

We plan to recruit subjects through mass mailings to zip codes within a 30-mile radius of the University of Pennsylvania, advertisements in local media, and flyers; methods that have been successful in our prior clinical trials. Inclusion criteria will be age 45-65 years and post-menopause, as defined by a history of amenorrhea for a minimum of 24 months and a serum FSH concentration of >25 mIU/mL. Exclusion criteria will be current or prior use of medications known to affect bone (i.e. bisphosphonates, calcitonin, selective estrogen receptor modulators, denosumab, diphenylhydantoin, or glucocorticoids), bone mineral density T score of less than -2.5 and greater than +2, vitamin D level less than 12 ng/ml, BMI of greater than 32, current alcohol or drug abuse, cardiac, pulmonary, liver, or renal disease or diabetes. Patients meeting the entry criteria at the screening or follow-up visit will be randomly allocated 1:1 to an active LMMS or a placebo device.

The PI and study staff will review subject accrual rates and adherence to inclusion/exclusion criteria on a monthly basis throughout the recruitment phase. Enrolled subjects who become subsequently ineligible will be reported. The recruitment strategies will be adjusted as needed to achieve the target subject characteristics. The PI and Safety Officer will review the data bi-annually to ensure that participants meet the goals outlined in the grant proposal.

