## **Background**

Weight bearing exercise has an osteogenic effect by reducing bone resorption and enhancing bone formation. During the past several years a number of articles have appeared demonstrating that low magnitude mechanical stimulation (LMMS) is osteogenic in animals and also in humans. The mechanobiology underlying these phenomena is beginning to emerge in terms of expression of genes stimulated by the action of the vibrations to which osteocytes are subjected. If successful, LMMS treatment, a non-pharmacologic intervention, could prevent bone loss and potentially stimulate bone formation resulting in increased bone strength and reduced fracture susceptibility in subjects at risk of developing osteoporosis. The proposed project focuses directly on measures of strength by evaluating the therapeutic response in terms of magnetic resonance (MR) image-based micro finite-element (FE) assessment of bone stiffness and failure strength, along with quantifying treatment-induced changes in marrow adiposity, as part of a single, integrated examination, conducted at baseline and 12 months of treatment in a double-blinded, randomized, placebo-controlled study of postmenopausal women. Special consideration will be given to compliance, which will be enhanced by an electronic feedback system.

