## **Key exclusion criteria**

Current and prior use of medications known to affect bone (e.g. bisphosphonates, calcitonin, selective estrogen receptor modulators, denosumab, diphenylhydantoin, or glucocorticoids) may be considered for exclusion, bone mineral density T score of less than -2.5 and greater than +2, vitamin D level less than 12 ng/ml, BMI of greater than 32, current alcohol or drug abuse (more than 3 alcoholic beverages per day or current use of illicit drugs or prescription medications), uncontrolled or untreated cardiac or pulmonary disease, liver disease (history of hepatitis or ALT or AST greater than 2x ULN), renal disease (history of renal disease or serum creatinine greater than 2x ULN), diabetes, Pacemaker or metallic implants (considered contraindicated to MR scanning).

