## **Subject recruitment**

Subjects will be recruited from a database of previous study participants as well as with outreach efforts to the university and general community via advertisements, letters and notices. These methods have been successful in prior clinical trials. Additionally, we will use the Penn Clinical Data Warehouse's (Penn Data Store) services.

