### Study Intervention

Active and placebo devices, previously manufactured by Juvent, Inc, will be available from a completed trial on children with Crohn's disease. The FDA has designated the risk pertaining to the device as "non-significant". Subjects will be stimulated mechanically for 10 minutes daily at a frequency of 30 Hz and acceleration of 0.3 g (fixed and not alterable by the subject). In a previous clinical trial involving postmenopausal women, there were no malfunctions detected during the entire year of the study. Upon their return, recalibration of the devices used in that trial showed 98% accuracy relative to start date calibration. To mask the active/placebo status of the devices, all devices are equipped with a small speaker that emits a 500 Hz audible tone. Adherence will be monitored by an inboard adherence monitor that documents date, time and duration of each use, and the adherence data will be transmitted via serial connector to a computer dedicated to this task and supervised by study's project manager. Subjects will also complete a web-based survey two days per week. Adherence feedback will be provided to study participants in bi-weekly intervals. Subjects will also be monitored in person during the six month and twelve month study visits to review adherence, supplementation compliance and to record adverse events.

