### Concomitant Medications

Patients who currently taking or who have previously taken medications known to affect bone such as bisphosphonates, calcitonin, selective estrogen receptor modulators, denosumab, diphenylhydantoin, or glucocorticoids will be considered for exclusion excluded from the study. In addition patients currently taking illicit drugs or abusing prescription medications will also be excluded. All medications will be reviewed and recorded during the screening visit. Any changes will be recorded at subsequent visits. The same applies to any change of dosage information (dose, frequency, route of administration) or indication.

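### Eligibility and follow-up screen bone-active drugs but neither exclude nor record use of LMMS or another vibration platform, before or during the trial

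*Combined protocol and SAP*

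**What the plan says.** Two sections list exclusions. Recruitment, screening, and eligibility criteria opens its list with "Exclusion criteria will be current or prior use of medications known to affect bone". Key exclusion criteria opens with "Current and prior use of medications known to affect bone", there worded as something that may be considered for exclusion. Both go on to T score, vitamin D, BMI, substance abuse, organ disease and diabetes, and the second adds contraindications to MR scanning. Concomitant Medications deals with drugs only: "All medications will be reviewed and recorded during the screening visit". None of the three mentions LMMS, the Juvent device or any vibration platform.

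Study procedures and the Schedule of visits and evaluations collect medical history and medications at screening, and review medical status, supplement compliance and daily routine at months 6 and 12. What the daily-routine review covers is not defined.

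On the intervention, the Background states that "low magnitude mechanical stimulation (LMMS) is osteogenic in animals and also in humans". Outcome analyses says that efficacy depends critically on adherence, and plans both a post-hoc exclusion of the least compliant quartile and a regression of effect on compliance. The only masking measure described, in Study procedures and Study Intervention, is a tone emitted by all devices.

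On recruitment, Subject recruitment says "Subjects will be recruited from a database of previous study participants as well as with outreach efforts to the university and general community", while the eligibility section says "We plan to recruit subjects through mass mailings to zip codes within a 30-mile radius of the University of Pennsylvania".

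**The concern.** The plan asks about past and present bone-active drugs, presumably because such exposure can alter the change in bone that the trial measures. On the protocol's own premise LMMS is also a bone-active exposure, and it is the one being tested, yet it is not screened. A coordinator who followed the lists as written would enrol a woman who uses a vibration platform at home or at a gym, or who has used an active LMMS unit.

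Three things are at stake:

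- **Dilution.** A placebo woman stimulated elsewhere during the year moves the placebo mean towards the active mean.
- **Misclassification.** The adherence monitor logs only the study unit. Stimulation from another platform is invisible to the compliance analyses.
- **Masking.** A woman who knows how an active unit feels may work out which device she has. That could affect her adherence, her retention and her reporting of symptoms.

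If the exposure is not recorded as it occurs, it cannot be reliably reconstructed after unblinding.

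**Working it through.** **1. Is the exposure caught anywhere?** The relevant sections, side by side:

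| Section | What it covers | Vibration or LMMS use? |
|---|---|---|
| Key exclusion criteria | drugs, T score, vitamin D, BMI, substance abuse, organ disease, diabetes, MR contraindications | no |
| Recruitment, screening, and eligibility criteria | the same, without MR contraindications | no |
| Concomitant Medications | medications and illicit drugs | no |
| Study procedures, screening visit | medical history, current medications | not named |
| Schedule, months 6 and 12 | medical status, supplement compliance, daily routine | not named |
| Study Intervention, Study Compliance | date, time and duration of use of the study device | study device only |

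No section excludes the exposure, prohibits it or names it as something to record.

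**2. Scale of the dilution.** The plan has no figure to reproduce: it states no effect size, SD or power. From the documents: 83 randomized to reach 64 completers, 1:1 allocation, two-sided 0.05, and an unpaired t-test on the 12-month change.

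Assumed here:
- 64/2 = 32 completers per arm.
- A true effect of d = 0.711 SD. This is not the protocol's figure. It is back-solved as the effect that a two-sample t-test with 32 per arm detects with 80% power.
- A share c of placebo women who each receive the full active effect from another source, with no change in SD.

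The placebo mean rises by c × d, so the contrast becomes d × (1 − c). The noncentrality parameter is d(1 − c) × √(32/2) = 4d(1 − c), on 62 degrees of freedom.

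| c | placebo women (c × 32) | d(1 − c) | 4d(1 − c) | power |
|---|---|---|---|---|
| 0 | 0 | 0.711 | 2.84 | 80% |
| 2% | 0.6 | 0.697 | 2.79 | 78% |
| 5% | 1.6 | 0.675 | 2.70 | 76% |
| 10% | 3.2 | 0.640 | 2.56 | 71% |

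A normal approximation with d = 0.70 gives the same rounded values (78.4%, 75.9% and 71.3%).

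**3. What this does not cover.** The table models only concurrent use in the placebo arm. Exposure before entry is a different mechanism: it matters only if it changes the later response. The documents give nothing from which to size that, so it is left unquantified.

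**The case against.** The strongest objection is that the frequency may be close to zero. A reader might put "Subjects will be recruited from a database of previous study participants" beside "In a previous clinical trial involving postmenopausal women, there were no malfunctions detected during the entire year of the study" and infer that former LMMS users are in the recruitment pool. The documents do not support that. They do not say which studies fed the database, or who ran the earlier postmenopausal trial. The one trial named as the source of the devices enrolled children with Crohn's disease. This objection stands, and the point does not rely on the inference: use of another platform during the year needs no link to the database.

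A reader might also infer that earlier exposure biases the comparison. Randomization balances it in expectation, the endpoint is within-subject change, and the regression adjusts for the baseline measurement. Gains made before entry are therefore largely absorbed, and only an altered later response would remain. This also stands.

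A third tempting reading is that the tone cannot blind an experienced user. The documents do not describe how the placebo platform feels or how perceptible 0.3 g is, so "may recognise" is as far as one can go. If the vibration is readily felt, masking is a general question that excluding prior users would not settle. The primary endpoint is image-based, and device use is logged electronically, so a change in adherence to the study unit would be visible.

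Finally, the power figures rest on an assumed effect, an assumed share and full equivalence of the outside stimulation to the study regimen. Weaker outside use would cost less.

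Medical history and the daily-routine review are existing places where the exposure could be captured, but neither names it. The objections limit the likely size of the problem; they do not close the gap.

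**Conclusion.** The gap is real, and its size is unknown. The plan screens bone-active drugs but neither excludes nor records use of LMMS or other vibration platforms, and does not ask participants to avoid such platforms during the trial. The main consequences are dilution and misclassification from concurrent use in the placebo arm, with possible recognition of the device by women who have used an active unit. Systematic confounding by earlier exposure is not shown.

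Under the stated assumptions the loss is about 2 percentage points of power if 2% of the placebo arm is fully contaminated, 4 points at 5% and 9 points at 10%. No value of the share can be taken from the documents, and it may be small. This is an inexpensive improvement that should be made, not a flaw that invalidates the design.

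**What to change.** 1. Add to both exclusion lists: current or recent use of a vibration platform, and prior use of an active LMMS device. The sponsor should set and justify the look-back window.
2. Ask about both in the screening history.
3. Instruct participants at the baseline visit not to use any other vibration platform during the trial.
4. Name outside platform use as an item in the daily-routine review at months 6 and 12, and record any use, so that the compliance analyses can take it into account.

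The cost is one eligibility line, one instruction and one question at visits that already take place. The downside is the loss of a few otherwise eligible women.

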#### Informed consent and HIPAA

Informed consent is an ongoing process, which is initiated at the first contact with the potential subject and the study team. The Study coordinator will provide a prospective volunteer with a brief explanation of the study in person or over the phone. If interested, the potential subject will schedule an appointment during which the combined informed consent and HIPAA authorization form will be reviewed and signed after all questions have been answered.

#### Randomization and blinding/unblinding procedures

Subjects meeting the entry criteria at the screening visit will be randomly allocated 1:1 to an active LMMS or a placebo device. The subjects will then be assigned a treatment number. Subjects name and study number will be kept in a password-protected database separate from other study records. Random numbers will be generated by a random number generator by the device manager who will maintain a database with even

numbers being assigned to treatment and odd numbers to placebo. This database will not be shared with the PI or other members of the study team before completion of the study.

### Study Intervention

Active and placebo devices, previously manufactured by Juvent, Inc, will be available from a completed trial on children with Crohn's disease. The FDA has designated the risk pertaining to the device as "non-significant". Subjects will be stimulated mechanically for 10 minutes daily at a frequency of 30 Hz and acceleration of 0.3 g (fixed and not alterable by the subject). In a previous clinical trial involving postmenopausal women, there were no malfunctions detected during the entire year of the study. Upon their return, recalibration of the devices used in that trial showed 98% accuracy relative to start date calibration. To mask the active/placebo status of the devices, all devices are equipped with a small speaker that emits a 500 Hz audible tone. Adherence will be monitored by an inboard adherence monitor that documents date, time and duration of each use, and the adherence data will be transmitted via serial connector to a computer dedicated to this task and supervised by study's project manager. Subjects will also complete a web-based survey two days per week. Adherence feedback will be provided to study participants in bi-weekly intervals. Subjects will also be monitored in person during the six month and twelve month study visits to review adherence, supplementation compliance and to record adverse events.

### Participant Retention

Data adherence with the prescribed LMMS regimen will be collected by the study team during the six month visit and the twelve month visit via a serial connector. The study team will be able to monitor the date, time and duration of each use. The Study coordinator will contact the subjects bi-weekly to discuss adherence and to provide support. Data will be summarized as the percent of prescribed number of minutes completed (percent adherence) in the study subjects. The study coordinator will contact all study subjects that fail to maintain an 80% adherence rate in order to identify obstacles to adherence and to develop strategies to improve adherence. The coordinator will review these data with the PI and study team on a monthly basis and reports will be provided to the safety officer quarterly.

### Concomitant Medications

Patients who currently taking or who have previously taken medications known to affect bone such as bisphosphonates, calcitonin, selective estrogen receptor modulators, denosumab, diphenylhydantoin, or glucocorticoids will be considered for exclusion excluded from the study. In addition patients currently taking illicit drugs or abusing prescription medications will also be excluded. All medications will be reviewed and recorded during the screening visit. Any changes will be recorded at subsequent visits. The same applies to any change of dosage information (dose, frequency, route of administration) or indication.

### Safety Reporting

Reports of any unexpected (headache, dizziness, blurred vision, motion sickness, abdominal pain, nausea, low back pain) and serious (events leading to hospitalization or death) adverse events will be prepared by the PI and sent to the safety officer, IRB, CTRC and NIAMS within 36 hours. Reports summarizing other adverse events will be prepared by the Sstudy coordinator and CTRC informatics and sent to the PI and safety officer bi-annually, as follows:

- Subjects will be asked to contact staff with any symptoms or complaints potentially related to the use of the LMMS device.
- Subjects will keep a written record of these symptoms or complaints in the same diary in which they record instances in which they are unable to use the LMMS device (e.g. vacation, illness).
- Adverse event data that are compiled bi-annually will capture any reported symptoms or complaints potentially related to the use of the LMMS device.

An adverse event form has been developed and will be used by the study staff to record any adverse events that may be related to the LMMS intervention. The clinical coordinator will prepare a summary of adverse events according to subject ID and the study statistician will generate a report of adverse event rates within

each study arm. These data will be provided to the PI and safety officer on a bi-annual basis. However, the PI and safety officer will remain blinded to treatment assignment unless the safety officer determines it is necessary to access this information.

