### **Safety issues**

Radiation: This research study involves exposure to radiation from the DXA and pQCT scans and therefore subjects will receive a small radiation dose. This radiation dose is not necessary for medical care and will occur only as a result of participation in the study. At doses much higher than subject will receive, radiation is known to increase the risk of developing cancer after many years. At the doses subject will receive, it is very likely they will see no effects at all.

Blood draw: The blood sampling process infrequently causes pain, bruising, bleeding, vein infection and/or vein clotting at the site, and possible fainting. There is little risk in providing five teaspoons of blood in a healthy individual.

MRI: The known risks associated with MRI are minimal. MRI uses radio waves and a magnetic field to take pictures. The magnet is always on. Some individuals may feel claustrophobic (uncomfortable in small spaces) during the MRI scan or may be disturbed by the sounds of the machine, which are loud and repetitive. Any metal objects on or inside the body may heat up, move and/or not function properly within the scanning room. To minimize any risk from these objects, MRI personnel will screen all subjects. Another risk is that from a metallic object flying through the air toward the magnet and hitting the subject. There are many safety measures in place to reduce this risk, including screening of all persons and materials entering the scanning room. In addition, as the study begins, the door to the room will be closed to minimize the risk of someone accidentally walking into or bringing an object into the magnet room. Some of the pulse sequences and/or RF coils are not FDA approved but are considered to pose no more than minimal risk. It is possible that during the course of the study, the research staff may notice an unexpected finding. Unexpected findings will be considered by the appropriate personnel and the PI will inform the subject if necessary. These possible findings may or may not be significant and may lead to anxiety.

Reproductive risks: Since DXA and pQCT involve radiation, a negative urine pregnancy test will be required before a woman of childbearing potential can participate in this study.

Juvent Vibration Platform: The FDA has designated the risk of the Juvent Vibration Platform as "non-significant".

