#### Data and Safety Monitoring Activities

The monitoring plan includes the case report forms (CRF) and source data verification of efficacy and safety parameters, the frequency of monitoring visits, regulatory document review, device accountability and compliance review. Monitoring will be conducted according to the University of Pennsylvania sponsor-investigator standard operating procedures.

A report schedule has been developed to meet the goals of the DSMP in accordance with NIAMS guidelines. The report forms are included below. The frequency of data review for this study differs according to the data type and is summarized in the following table.

Data Safety Monitoring Plan: Report Schedule			
Type of Report:	Prepared By:	Provided To:	Frequency:
Unexpected and Related Serious Adverse Events that Increase Risk	PI	Safety Officer, IRB, CTRC, NIAMS	Within 36 Hours
Adverse Events (combined)	Clinical Coordinator, CTRC Informatics Core	PI, Safety Officer IRB, CTRC	Every 6 months Annually
Patient Recruitment, Targets	Clinical Coordinator, CTRC Informatics Core	PI Safety Officer IRB	Monthly Every 6 months Annually
Subject Adherence with Intervention	Clinical Coordinator	PI Safety Officer	Monthly Every 6 months
Data Quality, Deviation from Protocol	Clinical Coordinator, CTRC Informatics Core	PI Safety Officer IRB	Monthly Every 6 months Annually and as needed
Final Analysis: Safety and Efficacy	Statistician	PI, Safety Officer	100% accrual and follow-up

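### The 36-hour safety report has no route for a harm that is neither a listed symptom nor leads to admission or death, and two sections state different triggers

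*Combined protocol and SAP*

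**What the plan says.** The Safety Reporting section sets the expedited rule and explains its two trigger words in brackets: "Reports of any unexpected (headache, dizziness, blurred vision, motion sickness, abdominal pain, nausea, low back pain) and serious (events leading to hospitalization or death". The first bracket is a list of seven symptoms, and the second names two outcomes only. Reports of these "will be prepared by the PI and sent to the safety officer, IRB, CTRC and NIAMS within 36 hours", which makes four recipients.

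All remaining events take the slower route. "Reports summarizing other adverse events will be prepared by" the coordinator and the informatics group, twice a year, for the PI and the safety officer. The scope of that compilation is limited: "Adverse event data that are compiled bi-annually will capture any reported symptoms or complaints potentially related to the use of the LMMS device". The adverse event form is likewise confined to events possibly attributable to the intervention.

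The Report Schedule table under Data and Safety Monitoring Activities has its own 36-hour row, with the same author, recipients and time limit. It describes the reportable events as "Unexpected and Related Serious Adverse Events that Increase Risk". It carries no symptom list and no definitions. Its row for combined adverse events goes to the PI and safety officer every six months and, as the table appears to read, to the IRB and CTRC annually.

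The Safety issues section lists no device effects. Its entry for the platform reads "The FDA has designated the risk of the Juvent Vibration Platform as" non-significant, and stops there.

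**The concern.** Expedited reporting is the only fast way for the safety officer and the oversight bodies to learn of a problem. Here both gates to it are narrow. One is a closed list, so an event that nobody thought to name cannot qualify as *unexpected*. The other depends on admission or death, so an important harm managed in a clinic or emergency department cannot qualify as *serious*. An event that fails both has no fast route.

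This matters for the trial in hand. Women with T-scores down to about -2.5 may enrol, they stand on a vibrating platform every day, and the visits are six months apart. A fall, a faint or a fracture is a plausible safety event, and many such events are treated without admission. The safety officer, who alone may decide to look at treatment assignment, could learn of one months later.

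The second problem is that two sections give different rules for the same report. Staff following one would send reports that staff following the other would not.

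**Working it through.** No arithmetic in the plan bears on this point, so the check sets the texts side by side.

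**Step 1: are the brackets definitions or examples?** Neither bracket carries *e.g.*, although the same section uses that abbreviation when it gives reasons for missing device use. No other section defines *unexpected* or *serious*, and none lists expected device effects against which unexpectedness could be judged. The brackets are therefore read as definitions.

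**Step 2: which events go out within 36 hours?** The word joining the two terms in Safety Reporting can mean either one or both together. The Report Schedule row is a third rule; since it does not define *serious*, the only meaning available is the one in Safety Reporting. Events are sorted by whether the symptom is listed and whether it led to admission or death.

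| Event | Safety Reporting: unexpected **or** serious | Safety Reporting: unexpected **and** serious | Report Schedule row |
|---|---|---|---|
| Listed symptom, no admission | Yes | No | No |
| Listed symptom, admission or death | Yes | Yes | Only if also unexpected, related and risk-increasing |
| Unlisted event, admission or death | Yes | No | Only if also unexpected, related and risk-increasing |
| Unlisted event, neither | **No** | **No** | **No** |

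The last line is the gap, and it is the same in all three columns. The first line is where the two sections visibly disagree: under the *or* reading, each headache or bout of back pain goes to four bodies within 36 hours; under the Report Schedule it does not.

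**Step 3: does copying one trigger into the other section cure it?** Put the Safety Reporting meanings into the Report Schedule row. *Unexpected* becomes one of the seven symptoms, and *serious* becomes admission or death. The row then covers only a listed symptom that leads to hospitalization or death, and even that must also be related and risk-increasing. An unlisted event that leads to admission drops out. Aligning the triggers while leaving the definitions alone therefore does not close the gap.

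**Step 4: what happens to an event in the gap?** If judged possibly device-related, it enters the six-monthly compilation. The longest wait for the safety officer is then about 6 months, or 6/12 = half of a participant's 12 months in the study. If judged unrelated, the form and the compilation, as worded, may not capture it at all.

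**The case against.** Several points on the other side are sound and set the limits of the finding.

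- **Over-reporting and under-reporting do not come from the same reading throughout.** A reader might infer that the rule both floods the recipients with minor complaints and misses every unlisted or non-admitted harm. The flood needs the *or* reading, and on that reading an unlisted event with admission is reported, as is a listed symptom without it. Only events that are both unlisted and not admitted or fatal escape.
- **The Report Schedule excludes a routine headache.** Its conditions are cumulative, so it removes the over-reporting. What remains is a disagreement between sections.
- **There is no conflict with Safety issues.** A reader might see a contradiction because the seven symptoms are missing there. Leaving them out of the risks and calling them unexpected is consistent. That they are foreseen is only an inference from their being named, and the consent pages, where device risks might appear, were not available.
- **Fracture is not an endpoint.** Fracture susceptibility appears in the Background as a possible benefit if the treatment works. The objectives and outcomes are stiffness, strength, bone density and marrow adiposity.
- **Staff would probably hear of the event.** The coordinator asks about adverse events on the bi-weekly calls, and participants are told to contact staff with device-related complaints. This shortens the time to staff awareness, but it does not trigger a report to the safety officer.
- **No burden can be calculated.** The documents give no incidence for any of the symptoms, so a count of extra reports would rest entirely on assumption.

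It may also be said that a wider meaning of *serious* comes from outside the documents. The gap itself does not depend on any outside standard: it follows from the plan's own words.

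**Conclusion.** The concern holds in this form. An event that is off the seven-symptom list and leads to neither admission nor death has no 36-hour route under either reading of Safety Reporting or under the Report Schedule row. Separately, the two sections state different triggers for the same report and must be reconciled.

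The size is a delay in notifying the safety officer of up to about six months for this class of event, with possible non-capture if the event is judged unrelated to the device. It is a weakness in safety oversight. It does not touch the efficacy analysis.

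The conclusion rests on two assumptions: that the brackets define rather than illustrate, and that *serious* in the Report Schedule means what it means in Safety Reporting. If the sponsor intended the symptoms only as examples and meant *or*, some unlisted outpatient events would qualify; the text does not say so. The stronger inference that the rule fails for any new kind of harm is not supported, because on the *or* reading an unlisted event leading to admission or death is reported.

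**What to change.** 1. State one 36-hour trigger and use it in both Safety Reporting and the Report Schedule, saying plainly whether the conditions are alternatives or cumulative.
2. Define *unexpected* as not consistent in nature, severity or frequency with a stated list of foreseeable device effects. Safety issues is the natural place for that list. Put the seven symptoms on it if the sponsor regards them as foreseeable.
3. Define *serious* by outcome, so that life-threatening, disabling and other important harms managed without admission are included. The sponsor should state how clinical fractures are classed.
4. Have the Report Schedule row refer to these definitions.

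The cost is a wording change in these sections, an IRB amendment, and a few more events reported within 36 hours. If the seven symptoms are classed as foreseeable, non-serious complaints of an expected kind would no longer need a 36-hour report under the *or* reading. No change to study treatment or visits is needed.
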